6.6.3 Safety data

With respect to safety evaluations, it is not planned to impute missing values.

The following approaches will be used for the descriptive reporting.

- Observed cases including escape medication (OC-IE) approach will include all collected data after escape medication use, without imputation for any missing data. Such an OC-IE approach will exclude all values measured after OL Spesolimab use at D8, or rescue medication with Spesolimab.
- Observed cases including intercurrent (OC-IR) approach will be applied in the same manner as defined for the efficacy data (see [Section 6.6.2](#)).

The only exceptions where imputation might be necessary for safety evaluation are AE dates and, start and stop dates for concomitant medications. Missing or incomplete AE dates are imputed according to BI standards (4).

Partial start and stop dates for concomitant medications, and background, escape, as well as historical medication for GPP will be imputed to enable subsequent calculation (but not for display) by the following "worst case" approach:

- If the day of the end date is missing, then the end date is set to last day of the month (or to the patient's trial completion date, if it is earlier than the last day of the month).
- If the day and month of the end date are missing then the end date is set to 31st of December of the year (or to the patient's trial completion date, if it is earlier than the 31st of December of the year).
- If the day of the start date is missing then the start date is set to first day of the month (except for escape medication, where the first dosing day will be used if first dosing happened in the same month).
- If the day and month of the start date are missing then the start date is set to 1st January of the year (except for escape medication, where the first dosing day/month will be used if first dosing happened in the same year).
- All other cases need to be assessed by the trial team on an individual basis, using the above points as guidance.

If a concomitant medication was ticked to be ongoing, it is expected that the end date is missing and will not be imputed for display purposes.

Missing start dates of open-label treatment with Spesolimab on Day 8 will be set to date of the Day 8 visit (if consistent with any specification on the month and/or year), otherwise it needs to be assessed by the trial team on an individual basis. Missing end dates will be set to the same date as the start date.

Missing start dates of rescue treatment with Spesolimab for a GPP flare will be set to the date of occurrence of the applicable flare, the date being consistent with any specification on month and/or year of the rescue treatment; other situations need to be assessed by the trial team on an individual basis.

6.6.7 Time since first diagnosis

For incomplete information on the date of first diagnosis, time since first diagnosis will be calculated as follows:

- If the year of first diagnosis is unknown, time since first diagnosis will be set to missing.
- If day and month of the first diagnosis are unknown, time since first diagnosis will be calculated as if diagnosed on the 30th June of that year.
- If only the day of the first diagnosis is unknown, time since first diagnosis will be calculated as if diagnosed on the 15th of that month.

6.6.8 Disease characteristics

Incomplete information regarding disease characteristics will be imputed as follows:

- For calculation of "date of diagnosis of most recent flare of GPP before the trial to Visit 1", partial dates will be replaced with the first day of the month (if month and year are available, and not later than the month and year upon which Visit 1 was performed). Otherwise, the dates will not be replaced. Replacement will only be done for calculation.
- For calculation of "start date of symptoms of current flare of GPP", partial dates will be replaced with the day of the first study treatment administration (if month and year are available, and are identical to the month and year upon which first study treatment administration was performed). Otherwise, the dates will not be replaced. Replacement will only be done for calculation.

6.7 BASELINE, TIME WINDOWS AND CALCULATED VISITS

Baseline, unless otherwise specified, refers to the last measurement collected prior to the dose of randomized Spesolimab/placebo administered at Day 1 in the study. For the analysis of biomarkers (see [Section 7.6.5](#)) baseline refers to the last measurement prior to randomized treatment administered at Day 1 but not more than 5 days earlier.

Measurements reported with date and time and taken prior to start of administration of trial treatment will be considered pre-treatment values. Measurements reported with a date only (and no time) and taken on the day of administration of trial treatment will also be considered pre-treatment values. These pre-treatment values will be assigned to visits according to the nominal visit number as recorded on the eCRF or as provided by the laboratory.

Measurements taken after start of administration of trial treatment will be considered either on- or off-treatment values based on the definition in [Section 6.1](#), and will be assigned to visits for statistical analysis, if applicable, as defined below.

Analysis of AE data, concomitant medications, recurrence of flares and of rescue/escape medication use will not be based on visits therefore, no assignment to time windows will be necessary.

All other safety, efficacy [REDACTED] measurements will be assigned to visits based on time windows around the planned visit dates, defined relative to the day of first trial treatment, Day 1. These time windows are defined in [Table 6.7: 1](#).

Table 6.7: 1 Time windows for assignment of efficacy, safety lab, vital signs [REDACTED]
[REDACTED] to visits for statistical analysis

Visit number	Visit label	Planned day	Time window		
			Window (per CTP)	Start (extended)	End (extended)
2	Week 1, Day 1	Day 1	exact day	Day 1 ^A	Day 1 ^A
3	Week 1, Day 2	Day 2	exact day	Day 2	Day 2
4	Week 1, Day 3	Day 3	exact day	Day 3	Day 3
5 ^B	Week 1, Day 4	Day 4	exact day	Day 4	Day 4
6 ^B	Week 1, Day 5	Day 5	exact day	Day 5	Day 5
7 ^B	Week 1, Day 6	Day 6	exact day	Day 6	Day 6
8 ^B	Week 1, Day 7	Day 7	exact day	Day 7	Day 7
9 ^E	Week 1, Day 8	Day 8	exact day	Day 8	Day 10
10	Week 2	Day 15	+/- 3 days	Day 11	Day 18
11	Week 3	Day 22	+/- 3 days	Day 19	Day 25
12	Week 4	Day 29	+/- 3 days	Day 26	Day 43
13	Week 8	Day 57	+/- 7 days	Day 44	Day 71
14	Week 12 ^C	Day 85	+/- 7 days	Day 72	Day 99
Post Week 12 ^D				Day 100	Day 113
Off treatment ^D				Day 114	Day of last follow-up value

All days are counted relative to the day of randomized treatment, which is defined as Day 1.

^A Note that measurements made at Day 1 and assigned to the on-treatment period (because mistakenly made after start of trial treatment) via assessment on date & time (i.e. safety laboratory) will not be assigned to Day 1. Such data will be listed only.

^B Since visits 5-8 are optional, the assessments (if any) will not be displayed in tables or figures only if otherwise specified.

^C Patients who receive rescue treatment with OL Spesolimab between Wk7-Wk12 will not have scheduled V14, however if there is any unscheduled assessment between the defined extended time window for V14, it will be still used.

^D All tables and figures by visit will only report visits up to week 12 (if applicable). “Post Week 12” and “off treatment” won’t be used for any tables or figures.

^E For primary analysis visit (V9), only the assessments prior any non-randomized treatment will be used except for those pre-specified post-treatment assessments.

Repeated and unscheduled efficacy, safety and other measurements will be handled similarly to scheduled measurements and will also be assigned to a time window depending upon the date of measurement.

Notice that for EN, EN-PC and EN-ID8 estimands, any observation post intercurrent events of interests (i.e., death, escape medication or rescue medication with Spesolimab for all 3 estimands or OL Spesolimab at D8 for EN and EN-PC only) will be set to be “non-response”. Further, within the extended time window of a visit, if the day of the intercurrent event is prior to the date of planned visit, then a “non-response” observation will be assigned to that day. If the day of the intercurrent event is on or after the date of planned visit, then a “non-response” observation will be assigned to that day only if there is no other observation on the same day, otherwise, no additional observation will be assigned.

Only one observation per time window will be selected for statistical analysis at a particular visit – the value which is closest to the protocol planned visit day will be selected. If there are two observations which have the same difference in days to the planned day, but which are not measured on the same day, the later value will be selected. If there are two observations on the same day, the worst value will be selected.

Assignment of observations to visits based on time windows will be based on the non-imputed (observed) data after the implement of estimand concepts. For example, for EN estimand, values after death or use of escape medication, OL Spesolimab at Day 8 or rescue medication with Spesolimab should be set to be “Non-response” first before assignment of efficacy endpoints.

For visits without an assigned value based on time windows, a value will thereafter be imputed (if needed) as defined in [Section 6.6](#). Imputation of efficacy endpoints, when applicable, will be performed based on all available observations meeting the imputation rules, irrespective of whether the observation was selected in any time window.

Tables and figures presenting results of the statistical analysis will only display visits at which the respective parameter was planned to be collected according to the CTP. Note that Visits 5-8 are optional so they will not be displayed in tables and figures only if otherwise specified.

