²Should a patient prematurely discontinue from the treatment, every effort should be made to keep the patient in the trial and complete all of the remaining study visits. If this is not possible, assessments at V9 (Wk1), V12 (Wk4), and EoS (V14 or V15 or V16 as applicable) should be completed or at a minimum an early EoS visit.

³If a patient qualifies for rescue treatment with open label BI 655130 at either a scheduled or unscheduled visit from after Day 8 and up to and including Week 12, all procedures/measurements listed for V9 (with the exception of skin biopsy, Whole Blood for RNA sequencing, Soluble Protein Biomarkers in Serum and Whole Blood for Flow Cytometry) are to be performed prior to dosing and an IRT call is to be placed prior to dosing.

⁴ C = Complete Physical Examination; T = Targeted physical examination. Refer to [Section 5.2.1](#) for additional details.

Clinical Trial Protocol

Proprietary confidential information © 2020 Boehringer Ingelheim International GmbH or one or more of its affiliated companies

⁵Per physician's assessment, Days 4 through 7 are optional if the patient has achieved complete pustular clearance (GPPGA pustulation sub score = 0) at the prior visit.

⁶Informed consent will be signed at the screening visit (V1). For patients completing V1 and V2 > 6 weeks apart, it is recommended that the patient is asked to re-confirm (verbally) his/her consent to participate in the trial at Visit 2.

⁷Infection testing includes tuberculosis, hepatitis B, hepatitis C, and HIV assessments (see [Table 5.2.3: 1](#)). EoS infection testing should only be done once at V14 or V15 or V16 as applicable.

⁸These procedures do not need to be repeated/Performed when V1 and V2 are performed on the same day.

⁹IL36RN mutation status is to be obtained from the patient's historical data if available.

¹⁰Vital signs: a) On non-study-drug administration days, vital sign assessments are to be done prior to blood sampling; b) On study drug administration days, vital signs will be assessed at pre-dose, at approximately 5 minutes after the end of infusion, and 120 mins after the end of infusion.

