Reactions to i.v. administered biologic agents represent the manifestations of systemic hypersensitivity reactions and include anaphylaxis, pruritus, hypotension and respiratory distress. Systemic hypersensitivity reactions are readily detectable, transient in nature, and manageable with standard medical treatment. Specific safety measures will be taken during

the trial. During and following the i.v. infusion, the patients will be monitored for systemic hypersensitivity including (See [Section 4.2.1.1](#) for further details) infusion reactions at the site according to Instructions for Preparation and Handling of BI 655130.

Based on the findings in the nonclinical studies conducted to date and in accordance with international regulatory guidelines, the inclusion of Women of Child Bearing Potential (WOCBP) in this study is justified. To minimize the risk on unintentional exposure of an embryo or fetus to the investigational drug, WOCBP must agree to the requirements for the pregnancy testing and contraceptive methods described in the protocol.

Although rare, a potential for drug-induced liver injury (DILI) is under constant surveillance by sponsors and regulators. Therefore, this trial requires timely detection, evaluation, and follow-up of laboratory alterations in selected liver laboratory parameters to ensure patients' safety, see also [Section 5.2.6](#).

Summary of benefit-risk assessment

The trial presents a benefit for the patient of monitoring until the next GPP flare as well as monitoring and careful management during and after the occurrence of that flare.

Considering the medical need of the development of an effective and well tolerated drug for treating GPP flares, the benefit of this trial is considered to outweigh the potential risks for and justifies the administration of BI 655130 to patients with Generalized Pustular Psoriasis (GPP) presenting with an acute flare of moderate to severe intensity. Due to the lack of mechanism- or compound-related safety signals and the antagonistic mode of action of BI 655130 it is considered likely that GPP patients will not be exposed to undue risks.

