5.2.2 Vital signs

Vital signs evaluations will be performed at visits as shown in the Flow Chart. This includes measuring temperature, pulse rate, systolic/diastolic blood pressure and respiratory rate. Respiratory rate, pulse rate, and blood pressure will be measured after patients have been sitting comfortably for at least 5 minutes. All recordings should be made using the same type of blood pressure recording instrument on the same arm if possible. Measurement of vital signs should precede blood sampling to avoid the impact of blood sampling on the vital measurements.

At visits with i.v. administration, vital signs will be assessed pre-dose, at approximately 5 minutes after the end of infusion and 120 minutes after the end of infusion. On non-study-drug administration days, vital sign assessments are to be done prior to blood sampling.

In addition to the temperature being measured along with the vital signs at time points shown in the Flow Chart, additional fever assessments will be recorded on dosing days at three time points. If the patient will receive medication for fever treatment, the fever assessment will be performed prior to taking the anti-fever treatment. These fever assessments must be taken whether or not the patient has an elevated temperature and whether or not the patient takes anti-fever treatment. The fever assessments times are to be separated by intervals of 2 to 4 hours on dosing days. At all other visits (non-dosing days), fever will be assessed once a day and will be completed prior to receiving medication for fever treatment, if anti-fever treatment is given.

During i.v. drug administration, patients should be closely monitored for signs and symptoms of hypersensitivity reactions for approximately 2 hours after the study drug administration.

Hypersensitivity reactions should be treated according to medical standards. Pre-medications for further infusions might be considered and will be agreed on between investigator and BI clinical monitor.

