6.2.2.1 Clinical monitoring after study drug administration

During i.v. drug administration, vital signs will be assessed pre-dose, at approximately 5 minutes after the end of infusion, and 120 minutes after the end of infusion. Patients should be closely monitored for signs and symptoms of hypersensitivity reactions for approximately 2 hours after doses are administered. Hypersensitivity reactions should be treated according to medical standards.

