7.8.3 Vital signs

The analyses of vital signs (blood pressure, pulse rate), body temperature, and body weight will be descriptive in nature. Descriptive statistics of vital signs over time and for the difference from baseline (see [Section 6.7](#)) will be provided, including the last value during the on-treatment period, the minimum value during the on-treatment period, and the maximum value during the on-treatment period (see [Table 6.1:1](#) for definition of the on-treatment period). Graphical displays via box plots will be produced for the change from baseline, over time, for each continuous vital sign endpoint.

[figure not shown]
Clinically relevant findings in vital signs data will be reported as baseline conditions (at screening) or as AEs (during the trial) if judged clinically relevant by the investigator, and will be analyzed as such.

[figure not shown]

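### SAP 6.7 gives the planned 5- and 120-minute post-infusion vital signs on Day 1 no analysis time point, so the one blinded, placebo-controlled infusion contrast is collected but not tabulated at those times

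*SAP*

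**What the plan says.** **Protocol.** Section 5.2.2 states that at visits with i.v. dosing "vital signs will be assessed pre-dose, at approximately 5 minutes after the end of infusion and 120 minutes after the end of infusion". Flow Chart footnote 10 and section 6.2.2.1 repeat the schedule. On what is measured, 5.2.2 says "This includes measuring temperature, pulse rate, systolic/diastolic blood pressure and respiratory rate". Section 6.2.2.1 sets these times beside a safety watch: "Patients should be closely monitored for signs and symptoms of hypersensitivity reactions for approximately 2 hours after doses are administered". Section 1.4 says reactions to i.v. biologics "include anaphylaxis, pruritus, hypotension and respiratory distress".

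**SAP 6.7.** Baseline is the last measurement before the randomized dose. For untimed values the rule is: "Measurements reported with a date only (and no time) and taken on the day of administration of trial treatment will also be considered pre-treatment values". Values taken after the start of treatment go to visits through Table 6.7: 1, whose title includes vital signs and which has one Day 1 row. Footnote A to that row says Day 1 values that fall after the start of treatment "will not be assigned to Day 1. Such data will be listed only". It describes them as taken late by mistake and names the safety laboratory. One observation is kept per window, and two on the same day resolve to the worst.

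**SAP exceptions.** Footnote E keeps pre-specified post-treatment assessments, but for Visit 9. SAP 7.8 sets post-treatment vital signs apart, but in a sentence about same-day data at open-label Day 8 or rescue dosing.

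**SAP 7.8.3.** It plans "Descriptive statistics of vital signs over time and for the difference from baseline", together with the last, minimum and maximum on-treatment values, for blood pressure, pulse rate, body temperature and body weight.

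**The concern.** Day 1 is the only infusion in the trial that is blinded and placebo-controlled; the Day 8 and rescue doses are open label. The readings at about 5 and 120 minutes are therefore the only randomized measurement of the acute effect of the infusion on blood pressure, pulse, temperature and respiration at fixed times. The protocol plans them for every randomized patient, yet the SAP has no row, window or table in which they appear as what they are.

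Two things are at stake. The first is a missing comparison: change from pre-dose to 5 and to 120 minutes, by arm. The second is conditional. If the database holds only a date for these readings, the SAP's own rule places post-infusion values before treatment, where they can compete to be the baseline for every later change-from-baseline summary of that parameter.

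**Working it through.** There is no plan figure to reproduce. The check is to follow a planned post-infusion Day 1 reading through each rule that could apply.

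**1. Number of readings.** Planned patients (protocol synopsis): 34 on BI 655130 and 17 on placebo. Post-infusion readings per patient on Day 1 (protocol 5.2.2): 2.
- BI 655130: 34 × 2 = 68 sets
- Placebo: 17 × 2 = 34 sets
- Total: 68 + 34 = 102 sets

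**2. Reading with a clock time, footnote A applied as worded on timing.** The treatment phase begins at the start of the infusion (SAP Table 6.1: 1), so the value is on-treatment. Footnote A then keeps it out of the Day 1 visit and sends it to a listing.

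**3. Reading with a clock time, footnote A confined to mistaken samples.** Nothing then bars the value from the Day 1 window. That window has one slot, all candidates fall on the same day, and the tie-break is the worst value. A pre-dose or post-dose reading could fill the slot without being labelled as such, and 6.7 gives no direction of worst for blood pressure or pulse.

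**4. Reading with a date only.** The date-only rule makes it pre-treatment. Pre-treatment values are placed by nominal visit number, which is Visit 2 for all three readings and does not separate them. Baseline is the last pre-dose value, but without times the last cannot be identified. The only same-day tie-break in 6.7 is the worst-value rule, and that is written for visit windows, so the choice of baseline is undefined.

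An invented example shows the direction of the effect. Take systolic pressure of 120 mmHg pre-dose, 90 at 5 minutes and 118 on Day 2.
- Change to 5 minutes: 90 − 120 = −30 mmHg
- Day 2 change from the pre-dose value: 118 − 120 = −2 mmHg
- Day 2 change if 90 is taken as baseline: 118 − 90 = +28 mmHg

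**5. Exceptions.** Footnote E and the SAP 7.8 sentence would each separate such readings, but neither reaches Day 1.

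**6. Summaries over time in 7.8.3.** These do not open another route. SAP 6.7 assigns every safety measurement outside its short list of exemptions (AEs, concomitant medication, flare recurrence, rescue and escape use) to visits through Table 6.7: 1, so over time means by visit.

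**7. On-treatment minimum and maximum in 7.8.3.** A timed post-infusion value is on-treatment and can enter these, unless the listing-only instruction removes it. The SAP does not say which prevails. The primary safety analysis runs to Day 85 and stops earlier at open-label Day 8 or rescue dosing (SAP 7.8). An extreme over that period is not tied to the two hours after the infusion, and patients given open-label drug at Day 8 contribute about one week while others may contribute up to 85 days.

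**8. Respiratory rate.** Protocol 5.2.2 collects it. SAP 7.8.3 does not list it, nor do the safety lists in the protocol synopsis and section 5.2.

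**The case against.** **Footnote A is about mistakes.** It is worded for samples taken late in error, with the safety laboratory as its stated case. A reader might infer that the SAP directs all post-dose Day 1 vital signs to listings only. The documents do not support that. The fair reading is that the SAP is silent on the planned readings, and footnote A is merely the only Day 1 rule within reach. This stands.

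**Some summary exists.** A reader might infer that post-infusion values are summarised nowhere. That is also too strong, because timed values are on-treatment and can reach the minimum and maximum. This stands, with the limits in working step 7.

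**Acute reactions are compared elsewhere.** All AE tables are repeated up to Week 1 (SAP 7.8). Systemic hypersensitivity is an AESI with its own search categories (SAP 7.8.1), and clinically relevant vital-sign changes are recorded as AEs. This stands and limits the consequence. It does not fill the gap: AE entry depends on the investigator's judgement, and AE onset time is not collected, so a Day 1 AE cannot be placed before or after the infusion.

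**Baseline contamination is hypothetical.** It needs a database with neither clock time nor nominal time point. SAP 7.8 separates post-treatment vital signs even where time is not collected, which suggests a nominal label may exist. This stands: the risk is conditional. The date-only rule still carries no exemption that uses such a label on Day 1.

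**Purpose is inferred.** The protocol places these readings next to hypersensitivity monitoring but never says they are taken for that reason. This stands.

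**Sponsor standards may cover it.** SAP 7.8 follows company standards that are not in the documents. That is possible, but those standards would still meet the assignment rules in 6.7.

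**Conclusion.** The gap holds in a limited form. No reading of SAP 6.7 gives the planned 5- and 120-minute Day 1 vital signs a correct analysis time point. Timed values are listed only, or compete for one Day 1 slot under a worst-value rule; untimed values count as pre-treatment. As planned, 102 sets of readings (68 active, 34 placebo) from the only blinded infusion are not summarised at their own times.

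The size should not be inflated. These are descriptive safety data, no hypothesis test is affected, and clinically relevant reactions still reach the AE and AESI tables by arm. It would be wrong to conclude that baseline is contaminated: the documents do not show what time information the eCRF records, and with a clock time, or a nominal time point used to separate the readings, the problem does not arise. The counts assume that all 51 planned patients are dosed and measured as scheduled. The respiratory-rate omission is a separate minor inconsistency.

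The change is worth making because the data are already planned and no other output gives this contrast.

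**What to change.** In SAP 6.7:
- Define vital-sign baseline as the planned pre-dose reading on Day 1.
- Exempt the planned 5- and 120-minute readings from footnote A and from the date-only rule.
- Assign them to their own Day 1 time points by nominal time point.
- State whether they enter the on-treatment minimum and maximum.

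In SAP 7.8.3:
- Add one descriptive table by arm of change from pre-dose to 5 and to 120 minutes on Day 1, for systolic and diastolic pressure, pulse rate and temperature.
- Reconcile respiratory rate with protocol 5.2.2: include it in 7.8.3 and in this table, or state why it is collected but not summarised.

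Before finalising, confirm from the eCRF specification whether a clock time or a nominal time point is held for each reading. The cost is a few lines of SAP text and one extra descriptive table from data already planned. No assessment, visit or clinical rule changes.
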